7.7 EXTENT OF EXPOSURE

There will be three methods of calculating exposure:

- a. First intake to last intake of study drug, including off-treatment periods
- b. First intake to last intake of study drug, excluding off-treatment periods
- c. Overall observational period (randomisation until end of follow-up for primary endpoint, see censoring for non-fatal events in [Section 6.8.3](#))

Descriptive statistics tables with mean, SD, median and range of the number of days a patient was on treatment will be provided. These tables will also provide the sum-total of the time (in years) that all patients were on treatment.

Frequency tables of number and percentage of patients belonging to categorical ranges of exposure weeks will be provided as well. Following are the categories of exposure-ranges (in days): >= 0 days, >= 30 days, >= 60 days, >= 83 days.

7.8 SAFETY ANALYSIS

The safety analysis will be based on the TS. Treatment will be evaluated as randomised.

While tables will generally display results by randomised treatment, listings will reflect whether a measurement/AE occurred on or off treatment.

7.8.1 Adverse Events

Unless otherwise specified, the analyses of AEs will be descriptive in nature and will be based on the number of patients with AEs and not on the number of AEs.

AEs will be coded using the current version of the Medical Dictionary for Regulatory Activities (MedDRA) coding dictionary.

Definitions of BI customised MedDRA Queries (BIcMQs) for new MedDRA versions are maintained by the BI dictionary maintenance group.

For analysis of multiple AE occurrences, data from the eCRF will be collapsed into an AE provided that all of the following applies:

- All AE attributes are identical (including Lowest Level Term (LLT), intensity, action taken, therapy required, seriousness, reason for seriousness, relationship, outcome, AE of special interest and also additional information of specific AEs or AESIs such as whether a bone fracture is traumatic).
- The occurrences were time-overlapping or time-adjacent (time-adjacency of 2 occurrences is given if the second occurrence started on the same day or on the day after the end of the first occurrence).

For further details on summarisation of AE data, please refer to [\(8\)](#).

7.8.1.1 Assignment of AEs to treatment

The analysis of adverse events will be based on the concept of treatment-emergent adverse events. That means that all adverse events occurring between first drug intake until 7 days after last drug intake will be assigned to the randomised treatment. All adverse events occurring before first drug intake will be assigned to 'pre-treatment' and all adverse events occurring after last drug intake + 7 days will be assigned to 'follow-up', except if otherwise specified.

In Section 15.3 of the CTR, general AE analysis tables will present only on-treatment AEs (applying the rule of 7 days for assignment as on-treatment) for the treatment groups.

Appendix 16.1.13.1 of the CTR will include an analysis (overall summary table, frequency of AEs by SOC / PT, frequency of SAEs by SOC/PT) where AEs and SAEs are assigned to the following phases: Screening, each treatment group, post-treatment for each treatment group.

For listings, AEs will be assigned to one of the following treatment phases: Screening, Placebo, Empa 10, Post Placebo, Post Empa, off-treatment.

7.8.1.2 AE summaries

An overall summary of adverse events will be presented.

The frequency of patients with adverse events will be summarised by treatment, primary system organ class and preferred term. Incidence rates as defined in [Section 7.8.1.7](#) will generally be included.

AEs will also be reported by intensity (without incidence rates). Separate tables will be provided for:

- for patients with serious adverse events,
- for patients with drug related serious AEs,
- for patients with AEs leading to discontinuation,

- for patients with drug-related AEs.

AEs leading to death will be listed.

The system organ classes, and preferred terms will be sorted by frequency (within system organ class).

Additionally, the following analyses will be reported in Appendix 16.1.13.1 of the CTR for disclosure on EudraCT and clinicaltrials.gov:

- Frequency [N (%)] of patients with non-serious adverse events occurring with incidence in preferred term greater than 5% by treatment,
- Adverse events per arm for disclosure on EudraCT by treatment
- Non-serious adverse events for disclosure on EudraCT by treatment
- Serious adverse events for disclosure on EudraCT by treatment

7.8.1.3 Adverse events of special interest (AESIs)

Hepatic injury

A frequency table of patients with hepatic injury as defined by the investigator on the eCRF tick box by treatment, primary system organ class and preferred term will be provided.

Hepatic injury AEs will be summarised based on a Standardised MedDRA Query (SMQ) based definition. From SMQ Drug related hepatic disorders (20000006) the following narrow sub-SMQs will be used:

- Narrow sub-SMQ Liver related investigations, signs and symptoms (20000008)
- Narrow sub-SMQ Cholestasis and jaundice of hepatic origin (20000009)
- Narrow sub-SMQ Hepatitis, non-infectious (20000010)
- Narrow sub-SMQ Hepatic failure, fibrosis and cirrhosis and other liver damage-related conditions (20000013)

A table with frequencies of patients with these AEs by treatment, primary SOC and preferred term will be provided. Hepatic injury SAEs based on the above SMQ definition will be presented.

Patients with hepatic injury will be listed.

For presentations on adjudicated hepatic events, refer to [Section 7.8.1.5](#).

Acute renal failure

A frequency table of patients with acute renal failure as defined by the investigator on the eCRF tick box by treatment, primary system organ class and preferred term will be provided.

A frequency table of patients with AEs related to acute renal failure by treatment, primary SOC and preferred term will be provided based on the narrow SMQ Acute renal failure (20000003).

SAEs and AEs leading to discontinuation based on the narrow SMQ Acute renal failure (20000003) will be presented.

In addition, frequency tables will be produced for patients with elevated creatinine $\geq 2 \times$ baseline and $> 1 \times$ upper limit of normal (ULN).

Patients with acute renal failure will be listed.

Ketoacidosis

A frequency table of patients with AEs related to ketoacidosis will be presented by treatment, primary SOC and preferred term for investigator reported cases and for the narrow and broad BIcMQ definition of diabetic ketoacidosis (DKA).

For presentations on adjudicated events, refer to [Section 7.8.1.5](#).

Patients with DKA based on the broad BIcMQ (30000019) or investigator reported ketoacidosis will be listed.

7.8.1.4 Specific AEs

Hypoglycaemic events

The investigator will record for each AE whether it represents a hypoglycaemic event and, if so, record additional information to assess the intensity of the hypoglycaemic event. On the basis of this information the hypoglycaemic event will be categorised as follows:

- severe hypoglycaemic episode: event requiring the assistance of another person to actively administer carbohydrate, glucagon or other resuscitative actions
- documented symptomatic hypoglycaemia with a measured plasma glucose concentration $< 3.0 \text{ mmol/L} (< 54 \text{ mg/dL})$: event accompanied by typical symptoms of hypoglycaemia but no need for external assistance
- documented symptomatic hypoglycaemia with a measured plasma glucose concentration $\geq 3.0 \text{ mmol/L}$ and $\leq 3.9 \text{ mmol/L} (\geq 54 \text{ mg/dL}$ and $\leq 70 \text{ mg/dL})$: event accompanied by typical symptoms of hypoglycaemia and no assistance required
- symptomatic hypoglycaemia and plasma glucose concentration $> 3.9 \text{ mmol/L} (> 70 \text{ mg/dL})$
- symptomatic hypoglycaemia and plasma glucose concentration not measured
- asymptomatic hypoglycaemia: event not accompanied by typical symptoms of hypoglycaemia but with a measured plasma glucose concentration $\leq 3.9 \text{ mmol/L} (\leq 70 \text{ mg/dL})$

Confirmed hypoglycaemic adverse events are defined as hypoglycaemic adverse events that had a plasma glucose concentration ≤ 70 mg/dL or required assistance.

Different tables will be shown for (i) patients with investigator-defined hypoglycaemia, and (ii) patients with confirmed hypoglycaemic adverse events, i.e. hypoglycaemic adverse events that had a plasma glucose concentration ≤ 70 mg/dL or required assistance.

In addition, the number of patients with hypoglycaemia according to SMQ (20000226) will be presented.

Patients with hypoglycaemic events will be listed.

Urinary tract infections (UTI) and genital infections

The following additional specific adverse events will also be assessed and be tabulated by treatment group:

- Genital infections (BICMQ narrow subsearch 1.1 “Genital tract infections predisposed to by glucosuria” (30000038))
- UTI (BICMQ narrow subsearch 2.1 “UTI predisposed by glucosuria” (30000041))

Complicated urinary tract infections defined as serious adverse events of BICMQ Infection narrow, subsearch 2.1 “UTI predisposed by glucosuria” (30000041), all events of subsearch 2.1.1 ‘Renal infections predisposed by glucosuria’ (30000042), all events of PT Urosepsis will be presented.

Complicated genital infection: defined as all serious events using the BICMQ Infection narrow subsearch 1.1 ‘Genital tract infections predisposed to by glucosuria’ (30000038) and all event of the subsearch ‘Complicated genital tract infections predisposed to by glucosuria’ (30000129) will also be presented.

Patients with UTIs or genital infections will be listed.

Bone fracture events

Frequency tables of patients with bone fracture by treatment, primary system organ class (SOC) and preferred term will be provided (based on the narrow BICMQ “Bone fractures” (30000008) and investigator reporting).

Investigator reported fractures will be reported overall and separately for each type of fracture (traumatic and non-traumatic).

Patients with bone fractures will be listed.

Urinary tract malignancy events

Urinary tract malignancy will be shown based on the BIcMQ – broad sub-search 14.1 ‘Urinary bladder and tract malignancies’ (30000057) and broad sub-search 14.2 ‘Renal malignancies’ (30000103):

Presentation of frequency will be done by treatment, high level term and preferred term.

Patients with urinary tract malignancy will be listed.

Volume depletion

Volume depletion will be based on the BIcMQ ‘Volume depletion of non-haemorrhagic cause and subsequent hypotension’ – narrow subsearch 2 ‘Volume depletion and hypotension due to dehydration’ (30000090).

A frequency table of patients with volume depletion by treatment, primary SOC and preferred term will be provided.

A separate table for serious volume depletion events will be presented.

Patients with volume depletion will be listed.

Hypotension

Frequency tables of patients with symptomatic hypotension as defined by the investigator on the eCRF tick box by treatment, primary system organ class and preferred term will be provided.

Symptomatic hypotension episodes will be presented by whether the intensity of diuretic medication was reduced and by whether the intensity of non-diuretic antihypertensive therapy was reduced.

A separate table for symptomatic hypotension events, which are serious, will be presented.

Additionally, hypotension by treatment, primary system organ class and preferred term will be provided. Hypotension is defined as preferred terms of the BIcMQ ‘Volume depletion of non-haemorrhagic cause and subsequent hypotension’ – narrow sub-search 2 ‘Volume depletion and hypotension due to dehydration’ (30000090) but excluding terms of the narrow subsearch 1 ‘Volume depletion due to dehydration’ (30000089).

A separate table for hypotension events, which are serious, will be presented.

Patients with hypotension events will be listed.

7.8.1.5 Events qualifying for external adjudication by the adjudication committee

An independent external CEC regularly reviews events and evaluates whether pre-specified criteria for these adjudication endpoints are met. Details on composition of the CEC, responsibilities and clinical event definitions are provided in the separate CEC Charter.

Adjudication assessments will be incorporated into the database.

Details of the adjudication process are described in the CEC charter.

Hepatic adverse events

Frequency tables summarising the relatedness and severity will be provided, including a listing showing the trigger events and adjudication results. This will include all adjudicated events up to 30 days after treatment stop.

Ketoacidosis

Frequency tables showing adjudicated certain ketoacidosis will be provided, including a listing showing the trigger events and adjudication results. This will include all adjudicated events up to 7 days after treatment stop.

7.8.1.6 AEs while patients taking wrong medication

A listing will be provided for AEs that occurred while a patient was taking the wrong study medication. If such a patient is identified, an additional adverse event table that assigns the adverse events to the actual treatment taken will be presented. A patient who took both the assigned treatment and at least one tablet of the wrong treatment, will be counted as at risk in both treatment groups for the respective relevant time. The table will include all adverse events by SOC and PT.

7.8.1.7 Adverse event incidence rates

For AE tables showing patients with events, in addition to the frequency tabulations, time-adjusted adverse event analyses will be performed for all AEs, investigator defined drug-related AEs, AEs leading to discontinuation, serious AEs, and adverse events of special interest by SOC and PT or High-Level Term (HLT) and PT, respectively.

The time at risk in patient years for the on-treatment phase is derived as follows:

Patients with AE:

time at risk (AE) in days = date of start of AE with specified PT/SOC/HLT – study treatment start date + 1

Patients without AE:

time at risk (AE) in days = end date of time at risk – study treatment start date + 1, where end date of time at risk is the minimum of date of last study drug intake + x days and date of death, if applicable.

The standard approach will be $x=7$ days, but for certain AESIs in addition other approaches will be used.

Total AE-specific time at risk per treatment group is then derived as:

Time at risk (AE) [years] = Sum of time at risk [days] over all patients in a treatment group/365.25

For 'each row of a table' (e.g. displaying an SOC), time at risk is calculated using start of first AE summarised in this row; e.g. for patients with an AE in a specified SOC, time at risk = date of start of AE with specified PT in this SOC – start of study treatment + 1.

The AE incidence rate per 100 patient years will then be calculated as follows:

Incidence rate per 100 patient years (pt-yrs) = $100 * \text{number of patients with AE} / \text{time at risk (AE) [years]}$.

In a similar way, the time at risk and incidence rate for the post-treatment period is derived. Here the start date is the start date of the post-treatment phase instead of the study treatment start date.

For some specific outputs showing number of episodes, event rates will be defined as number of episodes divided by time at risk. Time at risk will be the end date of time at risk – study treatment start date + 1, where the end date of time at risk is the minimum of date of last study drug intake + 7 days and date of death, if applicable.

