6. GENERAL ANALYSIS DEFINITIONS

6.1 TREATMENTS

There will be three basic treatment phases in this trial: screening, study treatment phase (with either empagliflozin 10mg or matching placebo) and post-treatment. However, during the study treatment phase, patients are allowed to go off-treatment and subsequently re-start treatment. This may happen not at all or repeatedly for a given patient.

The purpose of the definitions below is to describe all the different study/treatment intervals, in which a patient can participate in during the course of the trial. Note that the term "treatment regimen" also covers the "off-treatment" time periods.

Table 6.1: 1 Treatment regimens / study intervals

Label	Interval	Start date
Screening	Screening	Date of informed consent
Placebo/ Empagliflozin 10mg	Treatment	Date of first administration of study medication
Off-treatment (if applicable)	During treatment interval, but not on treatment	Date of last administration of study medication before temporary discontinuation + 1 day
Placebo/ Empagliflozin 10mg (if applicable)	During treatment interval, after restart of study medication	Date study medication re-started
Post-treatment	Post-treatment	Date of last administration of study medication + 1 day

Details on the definition of the on-treatment period for different endpoints are listed in [Table 6.1:2](#). The efficacy analyses will follow the intention-to-treat (ITT) principle in assigning patients to treatment groups, i.e. patients will be analysed as randomised.

Safety analyses will also assign patients to the treatment group as randomised.

If a patient erroneously receives the wrong trial drug, all subsequent medication packs dispensed to the patient will still be for the treatment group to which the patient was randomised. Therefore, the adverse events will be analysed as per randomised treatment, which is expected to reflect the prevailing treatment.

In the exceptional case that a patient took the wrong treatment, adverse events may occur while being on the wrong treatment. Analyses of this data are described in [Section 7.8.1.6](#).

Table 6.1: 2 Endpoint specific assignment to the on-treatment phase

Endpoint	Last day of assignment to the on-treatment phase (days after last intake of study medication)
Adverse events	7
Safety laboratory measurements	3
Heart rate	1
Glycosylated haemoglobin (HbA _{1c})	7
Glucose	1
Body weight	1
Creatinine and estimated glomerular filtration rate (eGFR)	1

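### Post-treatment AE rates: the only stated start of time at risk (last intake + 1 day) conflicts with the 7-day AE rule and, if applied, biases the rates low

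*SAP*

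**What the plan says.** SAP 7.8.1.7 derives the post-treatment rate by analogy with the on-treatment rate and changes one element: "Here the start date is the start date of the post-treatment phase instead of the study treatment start date". It names no day offset and no end date for the post-treatment time at risk.

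SAP 6.1 opens with "There will be three basic treatment phases in this trial: screening, study treatment phase" and a post-treatment phase. Table 6.1: 1 then gives the start of the post-treatment interval as "Date of last administration of study medication + 1 day". No other start date for post-treatment appears in the SAP.

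SAP 7.8.1.1 sets the counting rule for events. On the treatment side, "all adverse events occurring between first drug intake until 7 days after last drug intake will be assigned to the randomised treatment". On the other side, "all adverse events occurring after last drug intake + 7 days will be assigned to" the follow-up category. Table 6.1: 2 agrees, giving 7 days for adverse events as the limit of on-treatment assignment. The standard on-treatment time at risk in 7.8.1.7 also runs to last intake + 7 days, or to death if earlier.

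**The concern.** An incidence rate needs a numerator and a denominator that cover the same days. A reader who looks up the start of the post-treatment phase finds last intake + 1 day, yet an event can first count as post-treatment on day 8. The seven days between would enter the post-treatment denominator with no possibility of an event, and would also sit in the on-treatment denominator.

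Post-treatment observation in this trial is short, so seven days is a large share of it. The absolute post-treatment rates, and any comparison with the on-treatment rates, would mislead. Two programmers could also reasonably produce denominators that differ by up to seven days per patient.

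**Working it through.** The documents give no post-treatment rate or person-time, so there is no planned figure to reproduce. The check is person-time arithmetic.

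**Inputs.** L is the date of last intake; follow-up ends on day L + e.

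- Start as stated in Table 6.1: 1: L + 1.
- First day on which an AE can count as post-treatment (SAP 7.8.1.1): L + 8.
- Time-at-risk convention (SAP 7.8.1.7): end − start + 1.
- Completers: last dose at Visit 5 (Protocol 6.2.2) and follow-up call 7 days (+7) after the last dose (Protocol 6.2.3), so e runs from 7 to 14 if time at risk ends at the call. That end point is an assumption.
- Early discontinuers: followed to scheduled Visit 5, Day 90 (Protocol Flow Chart footnotes), so e = 90 − stopping day.

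**Formula.** For a patient without an event, the stated start gives e days and the matched start gives max(0, e − 7) days. The numerator is the same under both, so the understatement factor is e/(e − 7).

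| Patient | Days, start L + 1 | Days, start L + 8 | Factor |
|---|---|---|---|
| Completer, call on day 14 | 14 | 7 | 2.0 |
| Completer, call on day 12 | 12 | 5 | 2.4 |
| Completer, call on day 10 | 10 | 3 | 3.3 |
| Completer, call on day 7 | 7 | 0 | no eligible time |
| Stops Day 30, followed to Day 90 | 60 | 53 | 1.13 |
| Stops Day 60, followed to Day 90 | 30 | 23 | 1.30 |
| Stops Day 75, followed to Day 90 | 15 | 8 | 1.88 |

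For a patient with an event, time stops at onset. This changes little: with an assumed hazard of 0.01 per day and follow-up to day 14, the factor is 2.03.

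**Pooled rate (illustration).** Assume calls spread evenly over days 7 to 14 (mean 10.5 days, or 3.5 after removing 7). Assume early stoppers spread evenly over Days 5 to 83 (mean follow-up 90 − 44 = 46 days, or 39).

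- 75% completers: (0.75 × 10.5 + 0.25 × 46)/(0.75 × 3.5 + 0.25 × 39) = 19.375/12.375 = 1.57.
- 95% completers: (0.95 × 10.5 + 0.05 × 46)/(0.95 × 3.5 + 0.05 × 39) = 12.275/5.275 = 2.33.

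**Sensitivity.** Now let all completers be called on one day, and let discontinuers stop evenly over Days 1 to 89. As the call moves from day 14 to day 7, the pooled factor runs from 1.8 to 4.7 at 5% discontinuation, 1.7 to 2.8 at 10%, 1.5 to 1.9 at 20%, and 1.4 to 1.6 at 30%.

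**Other end dates.**

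- If only the start date is swapped and the stated end (last intake + 7 days, or death) is kept, post-treatment time ends before any event can count.
- If the day of trial completion in SAP 6.8.3 is used, its list of visit assessments omits the Visit 6 call. A completer without a later AE would then end at Visit 5 and contribute 0 days under either start.

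**The case against.** The best defence is that the SAP already implies a start at last intake + 8 days for AEs. SAP 6.1 refers to Table 6.1: 2 for endpoint-specific on-treatment periods, and that table gives AEs 7 days. SAP 6.7 treats measurements after the parameter-specific period as post-treatment. SAP 7.8.1.1 applies the 7-day rule and then lists AE phases as "Screening, each treatment group, post-treatment for each treatment group". SAP 7.8.1.7 itself runs the on-treatment phase to last intake + 7 days, so the next phase would naturally begin the day after. On that reading the factor is 1.0.

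This stands in part: it shows a conflict between passages rather than a plain error. It does not settle the matter. Table 6.1: 2 limits on-treatment assignment without dating the start of any phase, SAP 6.7 speaks of measurements, and 7.8.1.7 refers to a phase start date for which only + 1 day is stated.

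The objection on importance also stands. Safety analysis is descriptive with no hypothesis testing (Protocol 7.2.5), and the general AE tables show on-treatment events only. The split by phase is in an appendix to the trial report, and patient counts are unaffected. The same rule applies to both arms, so the comparison between arms changes little if discontinuation and follow-up are similar.

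**Conclusion.** The point holds as a conflict with a definite direction. Under the only start date the SAP states, the post-treatment denominator has up to seven days per patient in which no event can count, and any non-zero post-treatment rate is too low. Under the 7-day AE boundary there is no bias. The SAP does not say which applies.

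If time at risk ends at the Visit 6 call, the understatement is at least 2-fold for a completer called within the window and about 1.13-fold for a patient who stops on Day 30 and is followed to Day 90. The pooled factor is about 1.6 to 2.3 with 75 to 95% completers and calls spread evenly. The completion rates, stopping times and call timing are assumptions.

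A reader might infer that every post-treatment rate will certainly be understated two-fold or more. The documents do not support that: the start date is in conflict, the end date is missing, and two-fold is a figure for completers, not for patients who stop early and have long follow-up. Nor does any of this reach the primary analysis or the on-treatment AE tables.

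**What to change.** In SAP 7.8.1.7:

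- state that post-treatment time at risk for AEs starts at last study drug intake + 8 days, to match the 7-day assignment rule;
- state its end date: the patient's last AE-collection contact, including the Visit 6 call, or death;
- include only patients observed beyond last intake + 7 days.

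Table 6.1: 1 can stay as it is for its other uses. The cost is two or three SAP sentences and a small programming edit. The downside is that fewer patients contribute to the post-treatment table; a completer called on day 7 contributes nothing. If a start at + 8 days was already intended, the start-date sentence changes no result and removes the ambiguity.
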